## ***5.2 Entinostat***

All dose modifications should be based on the AE requiring the greatest modification and should be properly documented in source documents. Investigators may take a more conservative approach than the guidelines outlined below on the basis of clinical judgment that is in the best interest of the subject.

Management of toxicities that are at least possibly related to entinostat, with toxicities graded by the Investigator according to the NCI, CTCAE, version 4.03 should be managed as follows:

**Table 5: Dose Reductions for Entinostat-Related Non-Hematologic Toxicity**

Non-hematologic Toxicity	
Toxicity	Dose Modifications
Grade 4	
Administer symptomatic remedies/ start prophylaxis. Hold dose until recovery to Grade 1 or baseline under the following directions:
 
 
1. If recovered within 4 weeks of onset (ie: <math>\leq 3</math> missed doses) , resume study drug as follows: 
 
• If receiving 5 mg, restart study drug at 3 mg
 
• If receiving 3 mg, restart study drug at 2 mg
 
• If receiving 2 mg, discontinue study treatment
 
 
 
2. If not recovered within 4 weeks, permanently discontinue study drug.
 

Grade 3	
Administer symptomatic remedies/ start prophylaxis. Hold dose until recovery to Grade 1 or baseline under the following directions:
 
 
1. If recovered within 1 week, resume study drug at prior dose. If not recovered within 1 week, continue to hold dose.
 
2. If recovered within 2-4 weeks, resume study drug as follows: 
 
• If receiving 5 mg, restart study drug at 3 mg
 
• If receiving 3 mg, restart study drug at 2 mg
 
• If receiving 2 mg, permanently discontinue study drug
 
 
 
3. If not recovered within 4 weeks, permanently discontinue study drug.
 

Recurrence of the same $\geq$ Grade 3 toxicity despite dose reduction	
If the same <math>\geq</math> Grade 3 event recurs:
 
 
1. Administer symptomatic remedies/ start prophylaxis. Hold dose until recovery to Grade 1 or baseline.
 
2. If recovered within 2 weeks, resume study drug as follows: 
 
• If receiving 5 mg, restart study drug at 3 mg
 
• If receiving 3 mg, restart study drug at 2 mg
 
• If receiving 2 mg, permanently discontinue study drug
 
 
 
3. If the same <math>\geq</math> Grade 3 event recurs (i.e., third occurrence) despite entinostat dose reduction to 2 mg, as described above, discontinue study drug.
 

$\leq$ Grade 2	
Administer symptomatic remedies / start prophylaxis. Dosing of study drug may be interrupted at the Investigator's discretion.
 
 
• If dose is held for 4 consecutive weeks, permanently discontinue study drug.
 
• If toxicity resolves, resume entinostat at the original dose.
 

1: *If greater than 50% of doses are missed during any 6 week period, patients may be discontinued from study drug treatment, in the absence of extenuating circumstances.*

**Table 6: Dose Reductions for Entinostat-Related Hematologic Toxicity**

Hematologic Toxicity	
Toxicity	Dose Modifications

≥Grade 3 neutropenia, ≥Grade 3 uncomplicated thrombocytopenia, or Grade 2 complicated thrombocytopenia
	
Administer symptomatic remedies/ start prophylaxis. Hold doseP until recovery to Grade 1 or study baseline under the following direction:
 
 
1. If not recovered by next scheduled dose, skip the dose. If recovered by next scheduled dose, resume study drug at prior dose.
 
2. If receiving 2 mg dose, and not recovered by either of the next 2 scheduled doses, permanently discontinue study treatment. Otherwise, skip each dose. If recovered for either of these doses, resume study drug as follows: 
 
• If receiving 5 mg, restart study drug at 3 mg.
 
• If receiving 3 mg, restart study drug at 2 mg.
 
 
 
3. If not recovered within 4 weeks, permanently discontinue study drug.
 

Recurrence of the same hematologic toxicity
	
If the same hematologic toxicity recurs:
 
 
1. Administer symptomatic remedies/ start prophylaxis. Hold dose until recovery to Grade 1 or baseline.
 
2. If recovered within 2 weeks, resume study drug as follows: 
 
• If receiving 5 mg, restart study drug at 3 mg
 
• If receiving 3 mg, restart study drug at 2 mg
 
• If receiving 2 mg, permanently discontinue study drug
 
 
 
3. If the same ≥ Grade 3 event recurs (i.e., third occurrence) despite entinostat dose reduction to 2 mg, as described above, permanently discontinue study drug.
 

1: *If greater than 50% of doses are missed during any 6 week period, patients may be discontinued from study drug treatment, in the absence of extenuating circumstances.*

### 5.3 Hydroxychloroquine

#### 5.3.1 Dose Modification for Hydroxychloroquine

Any AE of ≥ Grade 3 and attributed as possibly, probably or definitely related to HCQ will result in the dose being held until the AE has resolved to ≤ grade 1 or baseline. If the AE resolves, reinstatement of treatment can occur at either the previous or reduced dose as described in Table 2 at the discretion of the investigator.

If the AE recurs at the reduced dose, treatment will be held until the AE has resolved to ≤ grade 1 and when resolved treatment can be reinstated at the next lower dose level.

Toxicities that may be attributable to HCQ include nausea, vomiting, diarrhea, rash, and visual field deficit. If any of these AEs occur at grade  $\leq 2$ , HCQ may be continued and the AE managed with supportive care. For any AE with a grade  $\geq 3$ , the dose of HCQ should be held until the toxicity resolves to grade 1 (or is found to be unrelated to HCQ).

With particular regard to visual field deficits patients should be cautioned to report any visual symptoms, particularly difficulty seeing entire words or faces, intolerance to glare, decreased night vision, or loss of peripheral vision. **These symptoms of peripheral retinal toxicity should prompt drug discontinuation and ophthalmologic evaluation.**

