#### ***4.5 DLT Definition and Escalation Decision Process***

Dose Limiting Toxicities will be defined by toxicity occurring during the first 4 weeks of this study. Any non-hematologic AE of Grade 3 or higher that is judged to be probably treatment-related will be considered a DLT with the exceptions of fatigue; rash attributable to regorafenib; or nausea, vomiting, or diarrhea that has improved to Grade < 1 within 72 hours. Any non-hematologic AE of Grade 4 or higher of any duration that is judged to be probably treatment-related will be considered a DLT except for elevations of lipase and/or amylase in the absence of clinical pancreatitis.

The following hematologic DLT will be considered if any occurs in the first cycle:

- 1) grade 4 neutropenia lasting more than 7 days
- 2) febrile neutropenia (T > 100.4 F in presence of ANC <500)
- 3) platelet count less than 25,000/mm^3
- 4) platelet count less than 50,000/mm^3 with clinically significant hemorrhage

If a DLT is observed in exactly 1 patient in the first cohort of 3, the cohort will be expanded to 6. If a DLT occurs in 2 or more patients per cohort, then the cohort one dose below will be the declared the MTD provided that at least 6 patients have been treated at that level with fewer than one third having DLTs. The rules for dose escalation and cohort size are outlined in Table 3. No intra-patient dose escalation is planned.

***Evaluable Patients:*** Patients will be evaluable for toxicity if they have taken one dose of HCQ and entinostat. Patients who experience a dose-limiting toxicity will be evaluable for the cohort after at least one dose of HCQ and one dose of entinostat. To be considered for evaluability in a Phase I cohort in the absence of dose-limiting toxicity, patients should have completed  $\geq 85\%$  of HCQ doses, and at least 3 of 4 entinostat doses. Phase II patients will be evaluable for response if they have completed 85% of their expected dose of HCQ and at least 3 doses of entinostat in the initial 4 weeks, in the absence of progression. Patients who do not meet these criteria will be replaced. In the unexpected event of excess toxicity at dose level 1, there is provision (Table 3) for a dose reduction of both HCQ and entinostat.

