6.3.4 Route of administration: Oral

6.3.5 Nursing/Patient Instructions: Hydroxychloroquine should be taken by swallowing the whole tablet in rapid succession without chewing. Patients receiving antacids, sucralfate, cholestyramine, and/or bicarbonate should have the HCQ drug dose administered at least 1 hour before or 2 hours after these medications.

6.3.6 **Table 10: Potential Toxicities of Hydroxychloroquine**

Central Nervous System	Irritability, nervousness, emotional changes, nightmares, psychosis, headache, dizziness, vertigo, seizure, ataxia, lassitude
Dermatologic	Bleaching of hair, alopecia, pigmentation changes (skin and mucosal; black-blue color), rash (urticarial, morbilliform, lichenoid, maculopapular, purpuric, erythema annulare centrifugum, Stevens-Johnson syndrome, acute generalized exanthematous pustulosis, and exfoliative dermatitis)
Gastrointestinal	Anorexia, nausea, vomiting, diarrhea, abdominal cramping
Hematologic	Aplastic anemia, agranulocytosis, leukopenia, thrombocytopenia, hemolysis (in patients with glucose-6-phosphate deficiency)
Hepatic	Abnormal liver function/hepatic failure (isolated cases)
Neuromuscular & Skeletal	Myopathy leading to progressive weakness and atrophy of proximal muscle groups (may be associated with mild sensory changes, loss of deep tendon reflexes, and abnormal nerve conduction)
Ocular	Disturbance in accommodation, keratopathy, corneal changes/deposits (visual disturbances, blurred vision, photophobia - reversible on discontinuation), macular edema, atrophy, abnormal pigmentation, retinopathy (early changes reversible - may progress despite discontinuation if advanced), optic disc pallor/atrophy, attenuation of retinal arterioles, pigmentary retinopathy, scotoma, decreased visual acuity, nystagmus

\*\*For complete information about hydroxychloroquine, please see the FDA package insert

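### Section 5.3.1 lets HCQ continue for a visual field deficit of grade 2 or lower, while its next paragraph has visual symptoms stop the drug; the list needs an exception

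*Combined protocol and SAP*

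**What the plan says.** Section 5.3.1 gives a grade-based rule for a named set of events: "Toxicities that may be attributable to HCQ include nausea, vomiting, diarrhea, rash, and visual field deficit". If any of these occurs at grade 2 or lower, "HCQ may be continued and the AE managed with supportive care". At grade 3 or higher, HCQ is held until the event improves to grade 1 "or is found to be unrelated to HCQ".

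The next paragraph turns to the eye: "With particular regard to visual field deficits patients should be cautioned to report any visual symptoms". It lists four kinds of symptom, among them loss of peripheral vision, and ends in bold: "These symptoms of peripheral retinal toxicity should prompt drug discontinuation and ophthalmologic evaluation". It sets no grade threshold.

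Neither paragraph refers to the other or says which prevails. The other HCQ text (the background in section 2.6, exclusion 3.2.7, Table 10 and Appendix A) supplies no exception or order of precedence.

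**The concern.** A patient with a grade 1 or 2 visual field deficit and symptoms falls under two neighbouring instructions. One permits continued dosing with supportive care. The other calls for stopping HCQ and examining the eye. An investigator who continued dosing could cite protocol text that names this very event.

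The protocol's own safety information favours stopping early. Table 10 describes retinopathy as "early changes reversible - may progress despite discontinuation if advanced", and section 2.6 says of chloroquine that stopping the drug can prevent it. Appendix A schedules no eye examinations, so detection rests mainly on patients' reports and on the adverse event questioning that section 8.5 requires at each contact. The instruction that follows a report should therefore be unambiguous.

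**Working it through.** The main check is a reading of the text. The plan states no figure on this point to reproduce.

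**1. The two paragraphs of section 5.3.1, case by case**

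| Situation | Grade-based list | Visual paragraph | Result |
|---|---|---|---|
| Nausea, vomiting, diarrhea or rash, grade ≤2 | May continue | Silent | Clear |
| Visual field deficit, grade ≤2, with a listed symptom | May continue | Stop and evaluate | Opposite actions |
| Visual field deficit, grade ≤2, no listed symptom | May continue | Action attaches to symptoms, so arguably silent | Permission stands alone |
| Listed visual symptom, no field deficit recorded | Not named | Stop and evaluate | Clear |
| Visual event, grade ≥3 | Hold | Stop and evaluate if symptomatic | Both interrupt HCQ |

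The defect is confined to the second and third rows.

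**2. How often it might arise**

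The documents give no event rate for this trial. Section 2.6 calls HCQ retinopathy infrequent, links it to prolonged exposure, and reports no overt retinopathy in 19 long-term users. Its risk marker is 730 g, which matches more than 5 years at 400 mg daily: 0.4 g × 365 × 5 = 730 g.

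For illustration, assume uninterrupted dosing for the overall survival times that section 2.5 reports for regorafenib (6.4 and 8.8 months), at 30.44 days per month. Exposure = daily dose × months × 30.44.

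| HCQ daily dose | 6.4 months | 8.8 months |
|---|---|---|
| 600 mg | 0.6 × 6.4 × 30.44 = 117 g (16% of 730 g) | 0.6 × 8.8 × 30.44 = 161 g (22%) |
| 1200 mg | 1.2 × 6.4 × 30.44 = 234 g (32%) | 1.2 × 8.8 × 30.44 = 321 g (44%) |

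These are not ceilings. Survival summaries for a group do not cap one patient's exposure, and section 4.6 sets no maximum duration. At 1200 mg daily, 730 g is reached after 730 / 1.2 = about 608 days. In the other direction, treatment stops at progression, so a typical patient should receive less than a survival-based figure implies.

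**3. Doses lost if HCQ is stopped while an evaluation is awaited**

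- *Cycle 1.* Section 4.5 makes Phase II patients "evaluable for response if they have completed 85% of their expected dose of HCQ", together with an entinostat minimum, in the first 4 weeks and absent progression. It sets the same HCQ percentage for Phase I patients without a dose-limiting toxicity. 0.85 × 28 = 23.8, so 24 full days are needed: 24/28 = 85.7% passes and 23/28 = 82.1% fails. Four missed days are allowed; five are not. In twice-daily doses, 0.85 × 56 = 47.6, so 48 are needed and 8 may be missed.
- *Cycle 2.* Section 4.3 asks for at least 80% of HCQ when judging chronic tolerability. 23/28 = 82.1% passes and 22/28 = 78.6% fails, so six or more missed days fail the criterion for that patient. The cohort requirement is 4 of 6 patients.

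**The case against.** The strongest reply is that the text runs from general to specific. The list offers a permissive default, and the very next paragraph singles out visual field deficits and states a bold rule. Because the default only permits continuation, an investigator who stops HCQ complies with both paragraphs. The two can also be separated by trigger: graded events in one, reported symptoms in the other.

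Much of this stands. The bold rule is evidently intended, a careful investigator would probably follow it, and the practical risk is small. Exclusion 3.2.7 further reduces it by keeping out patients with known macular degeneration or severe diabetic retinopathy. But the override is inferred, not written, and the list grants its permission to this event by name. Separating the paragraphs by trigger does not help either: it leaves a low-grade deficit without a listed symptom under the continue sentence alone.

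Two stronger readings are tempting and are not supported.

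- A reader might infer that the hold-and-reinstate rule at grade 3 or higher is also wrong. Both paragraphs interrupt HCQ at that grade, and the bold sentence does not say that stopping is permanent, so the two are compatible. What remains open is the route back to treatment.
- A reader might infer either a material threat to vision in this trial or, from the exposure figures, that 730 g cannot be reached. Section 2.6 describes an infrequent, long-exposure toxicity, and the 608-day calculation shows that the threshold is reachable for a patient who stays on treatment.

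**Conclusion.** The point holds as a minor correction to safety text. Section 5.3.1 permits continued HCQ for a low-grade visual field deficit, while the adjacent and evidently intended rule has visual symptoms stop the drug; no exception reconciles them. Harm would require an investigator to act on the list despite the bold sentence below it, or a deficit to come to light without any listed symptom.

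The expectation that this is rare rests on section 2.6 and on treating cumulative dose as the relevant measure. The 730 g marker comes from patients taking 400 mg daily, whereas this trial goes up to 1200 mg daily. The range of 117 to 321 g illustrates exposure at the reported survival times and bounds nothing. The sample size and the primary analysis method are unaffected.

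**What to change.** In section 5.3.1, make one of two edits:

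- delete visual field deficit from the grade-based list; or
- add to the continue sentence: *except visual field deficit and visual symptoms, for which HCQ is stopped and ophthalmologic evaluation obtained (see below)*.

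The second is more complete, because it also covers a deficit found without a listed symptom. Deletion removes the permission but gives no instruction for that case. Neither edit alters the rule at grade 3 or higher. Whether and when HCQ may be resumed after the evaluation is a separate clinical choice for the sponsor and is not part of this fix.

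The cost is a wording edit. The eye evaluation is already in the text, so no procedure is added. A few patients whose visual symptoms prove unrelated may miss HCQ doses, a cost that the bold rule already implies for symptomatic cases. Five or more missed days in cycle 1 fall below the 85% rule, and section 4.5 then says: "Patients who do not meet these criteria will be replaced". That consequence is not fully settled for response, because section 10.1 defines response evaluability without the 85% threshold. Six or more missed days in cycle 2 fail the 80% tolerability criterion for that patient. A prompt evaluation limits both.

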**Table 7: Dose Reductions for Regorafenib**

Drug	Starting Dose	Dose Level -1	Dose Level -2
Regorafenib	160 mg daily	120 mg daily	80 mg daily

## 6.0 DRUG INFORMATION

### 6.1 Regorafenib

- 6.1.1 Other names: BAY 73-4506
- 6.1.2 Commercial name: Stivarga
- 6.1.3 Availability: Regorafenib is commercially available as 40 mg tablets and is available through the hospital pharmacy
- 6.1.4 Route of administration: Oral
- 6.1.5 Storage and Stability: Regorafenib tablets are supplied in packages containing three bottles, with each bottle containing 28 tablets, for a total of 84 tablets per package. Store regorafenib at 25°C (77°F); excursions are permitted from 15 to 30°C (59 to 86°F). Store tablets in the original bottle and do not remove the desiccant. Keep the bottle tightly closed after first opening. Discard any unused tablets 28 days after opening the bottle. Dispose of unused tablets in accordance with local requirements
- 6.1.6 Nursing/Patient Instructions: Take regorafenib at the same time each day with a low-fat breakfast.

6.1.7 Table 8: Potential Toxicities of Regorafenib (from Stivarga Package Insert)

Adverse Reactions	STIVARGA (N=500)		Placebo (N=253)	
	Grade		Grade	
	All %	≥ 3 %	All %	≥ 3 %
General disorders and administration site conditions				
Asthenia/fatigue	64	15	46	9
Pain	29	3	21	2
Fever	28	2	15	0
Metabolism and nutrition disorders				
Decreased appetite and food intake	47	5	28	4
Skin and subcutaneous tissue disorders				
HFSR/PPES	45	17	7	0
Rash	26	6	4	<1
Gastrointestinal disorders				
Diarrhea	43	8	17	2
Mucositis	33	4	5	0
Investigations				
Weight loss	32	<1	10	0
Infections and infestations				
Infection	31	9	17	6
Vascular disorders				
Hypertension	30	8	8	<1
Hemorrhage*	21	2	8	<1
Respiratory, thoracic and mediastinal disorders				
Dysphonia	30	0	6	0
Nervous system disorders				
Headache	10	<1	7	0

\* Fatal outcomes observed.

Other clinically important adverse reactions observed more commonly in less than 10% of Stivarga-treated patients and at a higher incidence than in placebo-treated patients included the following: alopecia (7.6% vs. 1.6%), taste disorder (7.6% vs. 2.4%), musculoskeletal stiffness (6.0% vs. 2.0%), dry mouth (4.8% vs. 2.0%), hypothyroidism (4.2% vs. 0.4%), tremor (2.0% vs. 0.0), gastroesophageal reflux (1.4% vs. 0.0), and gastrointestinal fistula (0.8% vs. 0.4%).

Keratoacanthoma/squamous cell carcinoma of the skin occurred in 0.09% of 1100 Stivarga-treated patients across open-label or placebo-controlled clinical trials.

\*\*For complete information about regorafenib, please see the FDA package insert

## 6.2 *Entinostat*

- 6.2.1 Other names: MS-275, SNDX0275
- 6.2.2 Availability: Entinostat is not commercially available and will be supplied by Syndax at no cost to participants
- 6.2.3 Route of administration: Oral
- 6.2.4 Nursing/Patient Instructions: Entinostat is to be taken on an empty stomach, at least 2 hours after a meal and at least 1 hour before the next meal. If entinostat is vomited, dosing should not be re-administered but instead the dose should be skipped.

*For weekly (or less frequent) dosing:*

If an entinostat dose is missed, it may be taken up to 48 hours after the scheduled dosing time. If it is not taken within the 48 hour window, the dose should not be taken and should be counted as a missed dose. The patient should take the next scheduled dose per protocol.

- 6.2.5 Storage and Stability: Entinostat is an oral drug supplied by Syndax as pink to light red (1 mg) or yellow (5 mg) as polymorph B coated tablets. Each tablet contains mannitol, sodium starch glycolate, hydroxypropyl cellulose, potassium bicarbonate, and magnesium stearate as inert fillers. The film coating consists of hypromellose, talc, titanium dioxide, and ferric oxide pigments (red and yellow) as colorants. Entinostat is to be stored at controlled room temperature (15°C to 25°C) in a secure, locked storage area to which access is limited. Entinostat is to be protected from light and not to be exposed to extremes of temperature (greater than 30°C or less than 5°C). The pharmacist should dispense the investigational material to the patient at appropriate intervals throughout the study in childproof containers.

6.2.6 Table 9: Potential Toxicities of Entinostat

Adverse Events with Possible Relationship to MS-275 (SNDX-275, entinostat) (CTCAE 4.0 Term) [n= 215]		
Likely (>20%)	Less Likely (<=20%)	Rare but Serious (<3%)
BLOOD AND LYMPHATIC SYSTEM DISORDERS		
Anemia		
	Febrile neutropenia	
GASTROINTESTINAL DISORDERS		
	Abdominal pain	
	Constipation	
Diarrhea		
	Dyspepsia	
	Flatulence	
Nausea		
Vomiting		
GENERAL DISORDERS AND ADMINISTRATION SITE CONDITIONS		
	Edema limbs	
Fatigue		
	Fever	
	Non-cardiac chest pain	
INFECTIONS AND INFESTATIONS		
	Infection 	
INVESTIGATIONS		
	Alanine aminotransferase increased	
	Alkaline phosphatase increased	
	Aspartate aminotransferase increased	
	Blood bilirubin increased	
	Creatinine increased	
	Lymphocyte count decreased	
Neutrophil count decreased		
Platelet count decreased		
	Weight loss	
	White blood cell decreased	

Adverse Events with Possible Relationship to MS-275 (SNDX-275, entinostat) (CTCAE 4.0 Term) [n= 215]		
Likely (>20%)	Less Likely (<=20%)	Rare but Serious (<3%)
METABOLISM AND NUTRITION DISORDERS		
Anorexia		
	Dehydration	
	Hyperglycemia	
Hypoalbuminemia		
	Hypocalcemia	
	Hypokalemia	
	Hypomagnesemia	
Hyponatremia		
Hypophosphatemia		
MUSCULOSKELETAL AND CONNECTIVE TISSUE DISORDERS		
	Arthralgia	
	Back pain	
	Generalized muscle weakness	
	Myalgia	
	Pain in extremity	
NERVOUS SYSTEM DISORDERS		
	Dysgeusia	
Headache		
RESPIRATORY, THORACIC AND MEDIASTINAL DISORDERS		
	Cough	
Dyspnea		
	Epistaxis	
SKIN AND SUBCUTANEOUS TISSUE DISORDERS		
		Erythema multiforme
SURGICAL AND MEDICAL PROCEDURES		
	Surgical and medical procedures - Other (packed RBC transfusion)	

